7.3.2. Adverse Events (AEs)

Information will be summarized on all AEs that began at any time from the date of first study dose in Part A through the last procedure at the last study visit. Adverse events will be classified by the study Investigator into one of the following relations to study drug: not related, unlikely related, possibly related or related to study drug. For reporting purposes, "related" events will include all AEs assessed by the Investigator as: possibly related, or related to study drug.

All AEs captured in the eCRF will be coded using the Medical Dictionary for Regulatory Activities (MedDRA) coding system and displayed in tables and data listings using System Organ Class (SOC) and Preferred Term (PT). All AEs will be coded using the MedDRA, version 13.1 or higher.

Severity of AEs will be graded on a 3-point scale (mild, moderate and severe) based on the definitions, developed from Clinical Data Interchange Standards Consortium (CDISC) Study Data Tabulation Model (SDTM) standard terminology v3.1.1 (see Protocol Section 7.1.1).

Adverse event incidence will be reported based on the concept of treatment emergence for the purposes of this analysis. Any AE that occurs after the first dose of SBC-103 in Part A is considered a treatment emergent adverse event (TEAE) for this study.

Adverse events are summarized by patient incidence rates; therefore, in any tabulation, a patient contributes only once to the count for a given AE.

The number of events, as well as the number and percentage of patients with a TEAE, will be summarized by Part C dose assignment and overall, cumulatively over the entire study and separately for Part C.

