Study NGLU-CL02, *A Phase I/II Open Label Study in MPS IIIB Subjects to Investigate the Safety, Pharmacokinetics, and Pharmacodynamics/Efficacy of SBC-103 Administered Intravenously,* is an open label, 3-part Phase I/II study designed to evaluate the safety, tolerability, pharmacokinetics, and pharmacodynamics/efficacy of intravenous (IV) administration of SBC-103 in subjects with mucopolysaccharidosis III, type B (MPS IIIB, Sanfilippo B) with evaluable signs or symptoms of developmental delay.

Study NGLU-CL02 is conducted in 3 parts: Part A (Initial therapy at 0.3, 1, or 3 mg/kg), Part B (Extended Therapy at 1 and/or 3 mg/kg), and Part C (Extended Therapy at 5 and/or 10 mg/kg).

Part A is designed to assess the safety, tolerability, pharmacokinetics (PK), and pharmacodynamics (PD)/efficacy of 3 escalating doses of SBC-103 dosed once every other week (QOW) over 24 weeks.

Part B is designed to assess the safety, tolerability, PK, and PD/efficacy of chronic dosing for an extended period of time and to allow for intra-subject dose modification based on available data.

Following Part A and prior to entering Part B, subjects will have a 4-week period of time off therapy (instead of the usual 2 weeks between doses that occurs with QOW dosing) in order to assess the impact of treatment interruption on safety, tolerability, and select PD/efficacy markers, including the assessment of reversibility of any observed on-therapy changes in heparan sulfate (HS).

Part C (added with Amendment 6 and based on preliminary safety and PK/PD data from Parts A and B) is designed to assess the safety, tolerability, PK, and PD/efficacy of SBC-103 at 5 and 10 mg/kg QOW, as well as to assess the effects on chronic dosing. Subjects will be followed on Part C until the end of the treatment period at 156 weeks (a period of between 90 and 110 weeks). Intra-subject dose modification is permitted in Part C (based on data review and Sponsor agreement) with the intent to treat subjects with the lowest potentially efficacious dose that is safe and tolerable.

The protocol can be referenced for additional details. The Part C Schedule of Assessments (SOA) is attached in Appendix 9.1.4 of this Statistical Analysis Plan (SAP).

On 11 Jul 2017, Alexion decided to stop the clinical development program with SBC-103. A clinical study report (CSR) will detail the final demographic, disposition, exposure, and safety data of each study.

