4.1. Changes from Analyses Specified in the Protocol

The data analyses, data summaries and data presentations specified for the NGLU-CL02 CSR represent a reduced subset of the overall total data analyses, data summaries, and data presentations described in the NGLU-CL02 final approved Clinical Study Protocol (CSP) version (Amendment 7, 21 January 2016) for the full study. Only demographic, disposition, safety and exposure data will be used to create data summaries and listings for the reduced subset of the CSP specified full study parameters presented by Part C dose assignment (5 or 10 mg/kg

QOW) and overall (5 and 10 mg/kg QOW combined). Only the assessments/parameters specified in Section 4.1.4 will be included.

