5.2.1. Adverse Events (AEs)

Adverse events are defined in Protocol Section 7.1. Also refer to Appendix 9.4.3 of this SAP for special handling of AE partial dates. Any AE that occurs after the first dose of SBC-103 in Part A is considered a treatment emergent adverse event (TEAE). AEs will be summarized cumulatively over the entire study and separately for Part C.

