7. STATISTICAL ANALYSIS

All output will be sorted and labeled according to the International Conference on Harmonization (ICH) recommendations, and formatted to the appropriate page size(s).

For the analyses covered by this SAP, data analysis and presentation for this study is primarily descriptive in nature; therefore, no inferential analyses are planned. Selected data will be presented in by-patient data listings and summarized in tables across patients if appropriate.

Descriptive summaries will be presented for treated subjects overall and by dose assignment, as appropriate. Continuous data will be summarized using descriptive statistics including number of patients, mean, standard deviation (SD), median, minimum, maximum, Lower quartile (25th percentile) Q1, and Upper quartile (75th percentile) Q3; categorical data will be summarized by counts and proportions. No formal statistical hypothesis testing will be performed.

For this analysis, information will be displayed by the Part C dose assignment as follows: SBC-103 5 mg/kg – QOW and SBC-103 10 mg/kg – QOW. All data listings that contain an evaluation date will contain a relative study day (Rel Day). Pre-treatment and on-treatment study days are numbered relative to the day of the first dose of study drug which is designated as Relative Day 1. The preceding day is Day -1, the day before that is Day -2, etc. The last day of study drug is designated with an "L" (e.g., Day 14L).

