7.3.2.2. AEs and SAEs by System Organ Class (SOC) and Preferred Term (PT)

The number of TEAEs and the number and percentage of patients with events will be descriptively summarized and presented by SOC and PT. Patients are counted once in each SOC and PT. Percentages will be based on the total number of treated patients by Part C dose assignment and overall for each visit assessed.

The number of Serious TEAE's and the number and percentage of patients with events will be descriptively summarized and presented by PT. Patients are counted once in each PT. Percentages will be based on the total number of treated patients by Part C dose assignment and overall for each visit assessed.

All AEs will be presented in by-patient listings.

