7.3.2.5.2. Infusion-Associated Reactions

Infusion-associated reactions (IARs) will be considered AEs of special interest (AESIs). An AE will be considered an IAR if it meets either of the following criteria:

- The Investigator checks "Yes" to the question "Is AE an IAR?" on the AE eCRF.
- The AE (diagnosis and/or symptom) occurs between the start of the infusion up to 4 hours after the infusion and is assessed by the Investigator as at least possibly related to Investigational Medicinal Product (IMP).

Note that several AEs may be associated with 1 IAR observed with SBC-103 administration; each AE is captured as a separate event. The number and percentage of patients who experience any IAR and the number of IARs reported over the course of the study will be summarized. Any patient who experiences an IAR is only counted once regardless of the number of associated events. Patients may be counted more than once if IARs occur on more than 1 dosing day.

Summaries of AEs that comprise an IAR will be displayed by MedDRA PT. Each patient will be counted only once within each PT.

A by-patient data listing of all AEs will be presented.

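### The whole-study AE tables file events from 0.3, 1 and 3 mg/kg under the later Part C dose, and no table shows AEs at those three doses

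*SAP*

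**What the plan says.** SAP Section 7.3.2 sets the counting window: "Any AE that occurs after the first dose of SBC-103 in Part A is considered a treatment emergent adverse event (TEAE) for this study". It then says that event totals and patient-level incidence "will be summarized by Part C dose assignment and overall, cumulatively over the entire study and separately for Part C". SAP Section 5.2.1 repeats the two time frames: "AEs will be summarized cumulatively over the entire study and separately for Part C".

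The columns are fixed in SAP Section 7: "information will be displayed by the Part C dose assignment as follows: SBC-103 5 mg/kg", with 10 mg/kg as the second group. SAP Section 4.1 defines overall as the two groups combined. The system organ class and preferred term tables, and the serious TEAE table, use the same groups (SAP Section 7.3.2.2): "Percentages will be based on the total number of treated patients by Part C dose assignment and overall for each visit assessed". For IARs, SAP Section 7.3.2.5.2 says that "the number of IARs reported over the course of the study will be summarized", and SAP Section 7.3.2.1 includes patients with at least one IAR in the overall TEAE summary.

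SAP Section 4.1 discloses that the report covers a "reduced subset of the CSP specified full study parameters presented by Part C dose assignment". SAP Section 4 gives the background: the sponsor "decided to stop the clinical development program with SBC-103".

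Protocol Section 8.4 planned to tabulate AE and SAE severity and frequency by dose cohort, and IARs by cohort and overall. It allowed safety analyses by part or for the whole study and left details to the SAP.

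**The concern.** Safety and tolerability is the primary objective and the only one this SAP keeps. The study used five dose levels: 0.3, 1 and 3 mg/kg in Parts A and B, then 5 and 10 mg/kg in Part C. Every child started at 3 mg/kg or below.

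A cumulative table split by Part C assignment answers a question few readers will ask: what happened over the whole study to children who were later assigned to 5 or 10 mg/kg. With the columns headed by dose, it can be read as what happened at 5 and 10 mg/kg. The patient incidence of AEs, SAEs and IARs at 0.3, 1 and 3 mg/kg, which describes first-in-human exposure in children, is not tabulated at all.

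**Working it through.** There is no sample-size or power figure to reproduce here. The check is of table structure, followed by simple counts.

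**1. Subjects.** Part A cohorts as enrolled (Protocol Section 1.4.1): 3 + 4 + 4 = 11. Part C randomisation (SAP Section 9.3.2): 5 + 6 = 11. The totals agree, so all 11 children fall into one of the two columns.

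**2. Column for a Part A or B event.** An event after the first Part A dose is a TEAE. The whole-study table includes it. Its dose column is the child's Part C assignment. A Part A event at 0.3 mg/kg therefore appears under 5 or 10 mg/kg.

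**3. Whether another table shows the lower doses.** Taking the SAP safety sections in turn:

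| SAP section | Grouping |
|---|---|
| 7.3.1 Exposure | listings only |
| 7.3.2 and 7.3.2.1 Overall TEAE summary, including IARs | Part C assignment and overall; whole study and Part C |
| 7.3.2.2 SOC/PT and serious TEAEs | Part C assignment and overall |
| 7.3.2.3 to 7.3.2.5 Relationship, severity, deaths | by-patient listings |
| 7.3.2.5.2 IARs | over the study, by preferred term |
| 7.3.3.1 and 7.3.3.2 Laboratory, vital signs | listings only |
| 7.3.3.3.1 ADA; IARs by ADA status | Part C assignment and overall; ADA positivity |

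None is by Part A cohort, Part B dose or dose at onset. Even if the reference to visits in Section 7.3.2.2 means a by-visit breakdown, the columns are still Part C assignment.

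**4. Weight of one child.** If a child's only event of a given type arose before Part C, it adds 1/5 = 20.0 percentage points to the 5 mg/kg column or 1/6 = 16.7 points to the 10 mg/kg column.

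**5. Mix within columns.** Each Part C arm had to include at least one child from each Part A cohort. With cohorts of 3, 4 and 4 and arms of 5 and 6, five allocations are possible (numbers from the 0.3, 1 and 3 mg/kg cohorts):

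| 5 mg/kg arm | 10 mg/kg arm | Started at 0.3 or 1 mg/kg |
|---|---|---|
| 1, 1, 3 | 2, 3, 1 | 2 of 5; 5 of 6 |
| 1, 2, 2 | 2, 2, 2 | 3 of 5; 4 of 6 |
| 1, 3, 1 | 2, 1, 3 | 4 of 5; 3 of 6 |
| 2, 1, 2 | 1, 3, 2 | 3 of 5; 4 of 6 |
| 2, 2, 1 | 1, 2, 3 | 4 of 5; 3 of 6 |

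Both columns always contain all three starting doses.

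**6. Share of dosing before Part C.** Planned infusions are every two weeks at Weeks 0 to 24 (13) and Weeks 28 to 156 (65), so 13 + 65 = 78. SAP Section 4 gives 90 to 110 weeks in Part C, ending at Week 156.
- 110 weeks: Part C starts at Week 156 − 110 = 46. Part B doses at Weeks 28 to 44 number 9. Before Part C: 13 + 9 = 22, and 22/78 = 28%.
- 90 weeks: Part C starts at Week 156 − 90 = 66. Part B doses at Weeks 28 to 64 number 19. Before Part C: 13 + 19 = 32, and 32/78 = 41%.

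**7. Subtraction.** Whole-study events minus Part C events gives Part A plus B events, but under Part C assignment and not by 0.3, 1 and 3 mg/kg. Patient counts do not subtract: a child with the same event before and during Part C counts once in each table, so the difference is 0 although the child was affected earlier.

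**The case against.** The strongest defence is that nothing is hidden. Section 7.3.2 states both the window and the grouping, so a careful reader of the SAP can infer the mixing, and the columns are described as assignments. The Part C table isolates later events, and the overall column already exists. Every AE is listed by patient, target dose is listed by patient and visit, and with 11 children the dose at onset can be worked out by hand. Part C assignment is the only randomised grouping, and the report is descriptive and reduced because the programme ended. Columns by Part A cohort would have the mirror-image fault, placing 5 and 10 mg/kg events under 0.3, 1 or 3 mg/kg.

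Most of this stands, and it limits the harm. It does not supply the missing result, because neither the listings nor the Part C table tabulates patient incidence at the three lower doses.

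Three stronger readings are tempting and not supported:
- A reader might infer a breach of the protocol. Section 8.4 spoke of dose cohorts, did not promise dose at onset, and left details to the SAP.
- A reader might infer that IARs have no Part C analysis. The overall summary in Section 7.3.2.1 counts patients with an IAR and falls under the Part C cut in Section 7.3.2.
- A reader might infer that the 5 and 10 mg/kg percentages are inflated by 28% to 41%. That range is a share of planned infusions, not of events.

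**Conclusion.** The point holds as a reporting fault in the primary-endpoint tables that should be fixed. The whole-study dose columns do not describe experience at the doses in their headings, and three of the five dose levels have no table of AEs, SAEs or IARs.

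The size is bounded only in part. One child moves a column by 20.0 or 16.7 points. The 28% to 41% share of infusions assumes full dosing every two weeks to Week 156 and the SAP's 90 to 110 weeks in Part C; development was stopped on 11 July 2017, so actual shares may differ. The documents do not allow the actual effect on AE percentages to be calculated, and nothing here shows that any dose was more or less safe than the tables will suggest.

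**What to change.** 1. Present the cumulative whole-study AE, SAE and IAR tables in the existing overall column only. If the split is kept, footnote that the columns are Part C assignment and not dose at onset.
2. Add descriptive Part A/B tables of AEs, SAEs and IARs by the dose last received before onset (0.3, 1, 3 mg/kg), with the number of children and infusions at each dose.
3. Keep the Part C table by randomised assignment.

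The cost is a few lines of SAP text and a few extra tables, programmed from dated dosing and AE records already collected. The footnote alone costs almost nothing. AEs with partial onset dates need a stated rule, because SAP Section 9.4.3 imputes the earliest possible date and could move an event to an earlier dose.

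The added tables have limits that should be stated with them. They are sparse (the 0.3 mg/kg cohort has 3 children), a child can appear at more than one dose so rows do not add up to 11, and dose is confounded with time on study. They are descriptive only and support no dose-trend claim.

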3.1.3.1 Criteria for Dosing in Part C

The first subject who is eligible to dose escalate in Part C (see Section 4.3.4) and who is randomized to receive 5 mg/kg in Part C will be the first subject dosed in Part C; in the event that >1 subject is eligible at the same time, subjects will be dosed sequentially based on subject identification number (eg, Subject [Site #]-003 would be dosed before Subject [Site #]-005). As shown in Figure 3, the decision to continue dosing this subject and to start dosing the remaining 4 subjects at 5 mg/kg will be made by the Sponsor based on SRC recommendations after review of 24-hour safety data from the first subject dosed at 5 mg/kg. The remaining subjects randomized to the 5 mg/kg dose group may be dosed in parallel providing they meet all eligibility criteria to participate in Part C.

The decision to dose the first subject at 10 mg/kg will be made by the Sponsor based on SRC recommendations after review of safety data from 1 subject who completes the first 2 doses at 5 mg/kg, and review of all available safety data from any other subjects who have received at least 1 dose of SBC-103 at 5 mg/kg (Figure 3). Similar to initiation of dosing at the 5 mg/kg dose level, the first subject to receive the 10 mg/kg dose will be the first eligible subject to dose escalate in Part C who is randomized to the 10 mg/kg group; in the event that >1 subject is eligible at the same time, subjects will be dosed sequentially based on subject identification number. The decision to dose the remaining 5 subjects at 10 mg/kg will be made by the Sponsor based on SRC recommendations after review of 24-hour safety data from the first subject dosed at 10 mg/kg. The remaining subjects randomized to the 10 mg/kg dose group may be dosed in parallel providing they meet all eligibility criteria to dose escalate in Part C.

Intra-subject dose escalation from 5 to 10 mg/kg based on all available safety, PK, and PD/efficacy data may not occur without prior written approval from the Sponsor. Dose reductions may be considered for safety and tolerability at any time in Part C.

Page 49 of 121

Figure 3: Planned Subject Treatment and Dose Escalation Schedule in Part C (Therapy at 5 and/or 10 mg/kg)

Page 50 of 121

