Part C (added with Amendment 6 based on preliminary safety and PK/PD data from Parts A and B) is designed to assess the safety, tolerability, PK, and PD/efficacy of SBC-103 at 5 and 10 mg/kg over at least 24 weeks as well as to assess the effects on chronic dosing. Intrasubject dose modification is permitted in Part C (based on data review and Sponsor agreement) with the intent to treat subjects with the lowest potentially efficacious dose that is safe and tolerable. Because dose escalation occurs in Part C, 24-hour in-patient safety monitoring following the first dose for each subject and SRC and/or Sponsor review of safety data have been incorporated into Part C to minimize risk and to monitor subject safety (see Section 3.1.3.1). Additionally, in Part C, the SRC will continue to provide oversight of subject safety through periodic reviews of safety data. Ad-hoc reviews of safety data will be performed by the SRC on an as-needed basis in the event of emerging safety signals of clinical concern in one or more subjects, including subjects who meet pre-defined stopping rules (see Section 6.2).

To provide the greatest likelihood of benefit, subjects are permitted to enter Part C as soon as necessary regulatory and ethics committee review and approval (where required) has been obtained and the subject meets the qualifying criteria to begin dosing in Part C (see Section 4.3.4). Therefore, each subject's duration of treatment and assessments in Part B may vary. Once a subject enters Part C, the study visit schedule is reset to Day 0 Part C (Day 0C) to ensure that the visit days/assessments correspond to the same number of infusions of SBC-103 for each subject. All study visits in Part C will be scheduled relative to Day 0C to allow for a more meaningful assessment of the PK and PD/efficacy profile of the 5 and 10 mg/kg doses. In addition, subjects will be randomized such that at least 1 subject from each cohort assigned in Part A will receive SBC-103 at 5 mg/kg and at least 1 subject from each cohort assigned in

Part A will receive SBC-103 at 10 mg/kg. Thus each of the assigned dose levels from Part A will be represented in each of the 2 dose levels being studied in Part C.

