In addition, ongoing safety and PD data from Part C will be reviewed on an ongoing basis to guide further dose selection (ie, escalation from 5 to 10 mg/kg or reduction from 10 to 5 mg/kg) in this study with the goal of treating patients at the lowest dose that is likely to demonstrate clinical benefit while also being safe and tolerable.

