The subject should be restarted at a reduced dose. For example, if a subject was receiving a dose of 10 mg/kg, he/she would be restarted at 5 mg/kg; subjects receiving 5 mg/kg would be restarted at 3 mg/kg; etc. In the event that the subject was receiving a dose of 0.3mg/kg, he/she may resume at the 0.3 mg/kg dose only after AST or ALT have returned at least to baseline or to study nadir (nadir values may be confirmed by additional lab sampling at the discretion of the investigator, using the same lab for analysis of each sample), or normalized if the baseline level was within normal limits.

If after resuming treatment at the lower dose, the ALT or AST elevation recurs at greater than or equal to 2 times the ULN (for those with ALT or AST within normal limits at baseline) or 2 times the baseline value (for those with abnormal ALT or AST at baseline) study drug should be stopped and not resumed. Dosing will be paused based on confirmed elevations in AST or ALT with accompanying elevations in the following

• Confirmed bilirubin greater than 1.5 times ULN

- Confirmed INR increase of 0.2
- Eosinophilia (more than 5%), rash or fever

If these bilirubin and INR values normalize (and the independent SRC believes that it is safe to do so), the subject may resume dosing on a lower dose of the study drug (eg, those on a 3 mg/kg would resume dosing at 1 mg/kg, those on a 0.3 mg/kg dose would resume the 0.3 mg/kg dose). However, in this scenario, if a subject develops recurrent elevations in AST or ALT (with or without elevations in total bilirubin or INR), the drug should be stopped and not resumed.

Subjects whose rise in LFTs is accompanied by eosinophilia (more than 5%), rash or fever should not be restarted on the study drug.

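### Part C adverse events are tabulated only by assigned dose, so if a child changes dose within Part C, later events are counted under a dose no longer being given

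*SAP*

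**What the plan says.** SAP Section 7 sets the rule for all displays: "information will be displayed by the Part C dose assignment as follows", with two columns, 5 mg/kg and 10 mg/kg. Section 7.3.2 applies it to adverse events, whose event counts and patient percentages "will be summarized by Part C dose assignment and overall, cumulatively over the entire study and separately for Part C". Section 7.3.2.2 fixes the denominator: "Percentages will be based on the total number of treated patients by Part C dose assignment and overall for each visit assessed". Infusion-associated reactions (IARs) fall under the same rule. No summary uses the dose received or the dose at onset, and Section 7.2.1.5 lists no sensitivity analysis. The target dose at each visit appears only in a dosing listing (Section 7.3.1).

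The dose can change within Part C. SAP Section 4 allows this, subject to data review and Sponsor agreement. Protocol Section 3.3.3 foresees both directions: "escalation from 5 to 10 mg/kg or reduction from 10 to 5 mg/kg". Protocol Section 3.1.3.1 states: "Dose reductions may be considered for safety and tolerability at any time in Part C". It also allows escalation from 5 to 10 mg/kg with prior written Sponsor approval. After a pause for raised transaminases, Protocol Section 6.2.1 gives stepped-down restarts: "if a subject was receiving a dose of 10 mg/kg, he/she would be restarted at 5 mg/kg", and from 5 mg/kg to 3 mg/kg.

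**The concern.** Protocol Section 3.2 says that Part C is "designed to assess the safety, tolerability, PK, and PD/efficacy of SBC-103 at 5 and 10 mg/kg over at least 24 weeks". A reader will take the two columns of the Part C tables as the safety record of those two doses. Under the stated rule they are the record of what followed assignment to start at those doses.

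The difference is plainest for IARs, which SAP Section 7.3.2.5.2 largely defines by onset during an infusion or within 4 hours after it. The relevant dose is then the dose of that infusion. A reaction to a 10 mg/kg infusion in a child assigned to 5 mg/kg and later escalated would be counted under 5 mg/kg. The multiple-subject stopping rule in Protocol Section 6.2.2, by contrast, works on the dose at which subjects are treated.

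The point concerns dose changes inside Part C and the Part C tables. How the cumulative tables place Part A and Part B events is a separate matter.

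**Working it through.** The documents give no event rate, effect size, power or number of dose changes, so there is no figure of theirs to reproduce. The allocation is consistent: 5 + 6 = 11 (Protocol Section 6.7, SAP Section 9.3.2) and 3 + 4 + 4 = 11 (Protocol Section 1.4.1).

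**Weight of one child.** 1/5 = 20.0 points and 1/6 = 16.7 points. Suppose 1 of 5 and 4 of 6 children have an event at their assigned dose: 66.7 − 20.0 = 46.7 points. If one escalated child then has a first event at 10 mg/kg, the table shows 2/5 against 4/6: 66.7 − 40.0 = 26.7 points. The percentage moves only if the child had no earlier Part C event of that type, because a child counts once. The event count moves either way.

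**Share of infusions at another dose.** SAP Section 4 plans 90 to 110 weeks in Part C, which every other week gives 90/2 + 1 = 46 to 110/2 + 1 = 56 infusions per child. One of five children changing halfway puts 1/5 × 1/2 = 10% of the 5 mg/kg column's infusions at another dose; three of five put 30%.

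**Effect on the contrast (assumed rates).** Each column's rate is the sum over doses of (share of infusions at that dose) × (rate at that dose). Assume 0.05 events per infusion at 5 mg/kg; 0.075, 0.10 or 0.15 at 10 mg/kg (true ratios 1.5, 2, 3); and 0.04, 0.03 or 0.02 respectively at 3 mg/kg. Infusions per child are equal and risk depends only on current dose. Example for true ratio 2 with one escalation halfway: 0.9 × 0.05 + 0.1 × 0.10 = 0.055, and 0.10/0.055 = 1.82.

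| Dose changes in Part C | True 1.5 | True 2 | True 3 |
|---|---|---|---|
| None | 1.50 | 2.00 | 3.00 |
| 1 of 5, 5 to 10, halfway | 1.43 | 1.82 | 2.50 |
| 3 of 5, 5 to 10, halfway | 1.30 | 1.54 | 1.88 |
| All 5, 5 to 10, after a quarter | 1.09 | 1.14 | 1.20 |
| 2 of 6, 10 to 5, halfway | 1.42 | 1.83 | 2.67 |
| 3 of 5 up and 2 of 6 down, halfway | 1.23 | 1.41 | 1.67 |
| 2 of 5, 5 to 3, halfway | 1.56 | 2.17 | 3.41 |

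With the same rate at every dose the ratio is 1.00 in every row.

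**Which denominator the added table needs.** Assume instead a Part C incidence of 20% at 5 mg/kg and 60% at 10 mg/kg with constant hazards: h5 = −ln 0.8 = 0.223, h10 = −ln 0.4 = 0.916. Half of Part C at 5 mg/kg carries risk 1 − exp(−h5/2) = 10.6%; half at 10 mg/kg carries 1 − exp(−h10/2) = 36.8%. If all five escalate halfway, a by-dose table that divides by children ever dosed shows 10.6% at 5 mg/kg and (6 × 60% + 5 × 36.8%)/11 = 49.4% at 10 mg/kg, instead of 20% and 60%. It keeps most of the gap but understates both levels, because a child with few infusions weighs as much as one with many. Events per infusion, or per patient-time, recover the assumed rates if switching is unrelated to risk.

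**The case against.** A reader might infer that counting by assignment always shrinks the dose contrast. The documents do not support that. The restart from 5 to 3 mg/kg in Protocol Section 6.2.1 widens it if risk rises with dose, and a flat relation leaves it alone.

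The reduction side is also weaker than it looks. An event that triggers a change from 10 to 5 mg/kg occurred at 10 mg/kg and is already counted there. Under the 20% and 60% assumption with 2 of 6 children reduced halfway, the by-assignment gap is 54.5% − 20.0% = 34.5 points. A table by dose received over children ever dosed gives 52.2% − 17.3% = 35.0 points after rounding, a gain of about 0.5 points in child percentages.

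Nor are dose changes simply a product of the safety outcome. Escalation rests on safety, PK and PD/efficacy data together, so a weak PD response may drive it. Assignment is the randomised grouping, while a grouping by dose received is open to selection. The analysis is descriptive with no inferential comparison (SAP Sections 7 and 7.2.1.4). With 11 children, the listings allow events to be matched to doses by hand.

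All of this stands, and it limits the size of the point and shapes the remedy. It does not remove the point. The SAP's own rule places an event under an assigned dose whatever dose was given. The hand reconstruction means joining two listings, and the event listing is not said to carry the dose.

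**Conclusion.** The concern holds in conditional form. The by-assignment rule can misplace Part C events whenever a child changes dose, and the SAP provides no second display. The direction depends on which changes occur and on whether risk rises with dose. The ratios and incidences above rest on assumed event rates and switch times. The 20- and 16.7-point steps follow from the column sizes alone. The actual effect may be zero, because neither document reports that any child changed dose in Part C.

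A reader might also conclude that safety by dose is the only question left in the reduced report, or that the antibody tables have the same Part C fault. Neither follows. The SAP objective is overall safety and tolerability (Section 4.1.1), an overall column is planned, and antibody status is related to IARs. Section 7.3.3.3.1 defines no Part C-only antibody table. The change is worth making because it is cheap and the columns will be read as dose-specific.

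**What to change.** Keep the by-assignment tables. In SAP Sections 7.3.2 and 7.3.2.5.2:

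- Add Part C tables of TEAEs, TESAEs and IARs by the dose of the most recent infusion begun before onset, with a column for a lower dose if one was used. Show events per infusion (or per patient-time) at each dose beside the child counts.
- Add dose at onset to the by-patient adverse event listing.
- Report how many children changed dose in Part C, when and why. If none did, one sentence saying so closes the matter.
- Add a caution that rates by dose received are subject to selection, because safety and PD data drive the changes.

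The cost is one derived variable and some extra tables. Target dose by visit and infusion start and stop times are already listed (SAP Section 7.3.1), and events within 24 hours of an infusion carry a time as well as a date (Protocol Section 7.3). A child who changes dose appears in more than one column, which needs a footnote.
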